**SCHEDULE OF MANDATORY EVENTS**

	Screening, Baseline and Randomization	Antepartum: Week 20 ± 4 weeks visit	Labour & Delivery*	6-12 weeks Postpartum
Inclusion/Exclusion	✓			
Consent	✓			
Randomization	✓			
Demographic	✓			
Med/ObGyn Info/History	✓			
Blood work	✓			
Dating ultrasound	✓	✓		
Concomitant Medication	✓	✓	✓	✓
Treatment Compliance		✓		✓
Drug Regime**		✓		✓
Labour & Delivery Data			✓	
Infant Health			✓	
Epidural Use				✓
Outcome Information		✓	✓	✓
Adverse Events		✓	✓	✓

1 – BhCG is required to document current pregnancy, if not previously available. A complete blood count and creatinine will be drawn, if not previously available within the past 3 months. Lupus anticoagulant, anticardiolipin IgG and IgM antibodies and beta-2 glycoprotein IgG and IgM antibodies (if available) will be drawn to confirm eligibility if required, as well as bloodwork stored for central lab testing.

2 – Dating ultrasound results will be recorded, if available. An obstetrical ultrasound is recommended within 7 days of study enrolment as a baseline, starting at 6-7 weeks gestation.

3 – Outcome events will be recorded up to 6 weeks postpartum

4 – Adverse events requiring medical intervention will be followed until resolution or up to 90 days in which the AE will be considered chronic (at the discretion of the investigator).

\* – Labour and delivery data will be gathered retrospectively by medical chart review. Any additional information and details required will be gathered by patient recall at the postpartum follow-up visit.

\*\* – As applicable.

**ABBREVIATIONS AND DEFINITIONS OF TERMS**

AE	Adverse Event
ASA	Aspirin
APS	Antiphospholipid syndrome
AT	Antithrombin
bid	Twice Daily
BP	Blood Pressure
CBC	Complete Blood Count
DBP	Diastolic Blood Pressure
DVT	Deep Vein Thrombosis
IUGR	Intrauterine Growth Restriction
LMP	Last menstrual period
LMWH	Low Molecular Weight Heparin
o.d.	Once Daily
PE	Pulmonary Embolism
PIH	Pregnancy Induced Hypertension
RCT	Randomized Clinical Trial
RFTs	Renal function tests
SAE	Serious Adverse Event
SBP	Systolic Blood Pressure
SLE	Systemic Lupus Erythematosus
U/S	Ultrasound
ULN	Upper Limit of Normal
VTE	Venous Thromboembolic Event
Wk	Weeks

## **1. BACKGROUND**

### **1.1 Why is a randomized clinical trial (RCT) needed?**

Women with APS are at increased risk of pregnancy loss compared to the general population. The current standard of care, outlined in the CHEST guidelines, is to give antepartum prophylactic-dose LMWH and aspirin (ASA) to prevent future pregnancy loss. Specifically, the CHEST guidelines mention “For women who fulfill the laboratory criteria for APLA syndrome and meet the clinical APLA criteria based on a history of three or more pregnancy losses, we recommend antepartum administration of prophylactic- or intermediate-dose UFH or prophylactic LMWH combined with low-dose aspirin, 75 to 100 mg/d, over no treatment”. In contrast, the Society of Obstetrics and Gynecology of Canada (SOGC) clinical practice guidelines recommend “Low-dose acetylsalicylic acid or low-dose acetylsalicylic acid plus low molecular weight heparin is recommended in pregnant women with confirmed antiphospholipid syndrome”

These guideline recommendations vary, and are based on trials with significant methodological flaws. Three trials showed improved live birth rates with unfractionated heparin/ASA versus ASA alone. Kutteh published a single-center non-randomized trial of 50 patients with at least 3 pregnancy losses and positive anticardiolipin antibodies, alternatively assigned to PTT-adjusted heparin or not. There was a significant difference in live birth rate (80 versus 44%), however, the non-randomized study design significantly limits interpretation of these results. Rai et al. completed a randomized trial of 90 patients with a history of 3 consecutive pregnancy losses and positive lupus anticoagulant or anticardiolipin antibodies (IgG > 5 GPL or IgM > 3 MPL) tested over 8 weeks apart, randomizing women to antepartum unfractionated heparin 5000 units sc Q12H and ASA versus ASA alone. The live birth rate was improved, from 71 versus 42%. Lastly, Goel et al. included a subset of 72 patients within a larger trial of 450 pregnant women with a history of 2 pregnancy losses and positive anticardiolipin antibodies. Patients who received unfractionated heparin/ASA during pregnancy had improved live birth rate (84.8%) versus ASA alone (61.5%). Both trials were limited by small sample sizes and varying definitions of positive anticardiolipin antibodies.

In contrast, two subsequent trials evaluated LMWH/ASA versus ASA alone found no difference in live birth rates. Farquharson et al. randomized 98 women with at least 3 consecutive pregnancy losses or 2 pregnancy losses with proven fetal death after 10 weeks gestation with persistently positive lupus anticoagulant and/or anticardiolipin antibodies at least 6 weeks apart. Women were randomized to antepartum LMWH/ASA versus ASA alone until delivery. There was no difference in live birth rate between treatment arms (78% versus 72%, p=0.49). One limitation to this study is a 25% reported crossover rate between study arms, based on physician or patient preference. Lastly, Laskin et al. completed a randomized trial of women a history of 2 or more pregnancy losses, including patients with one of: ANA positivity, lupus anticoagulant or anticardiolipin antibodies, or inherited thrombophilia, randomizing participants to LMWH/ASA versus ASA alone during pregnancy. Of the subgroup with lupus anticoagulant or anticardiolipin antibody positivity, there was no difference in the live birth rate (77% versus 75%) among 42 patients. Laskin et al. conclude “these findings contribute to the growing body of literature that contests the emerging standard of care comprising LMWH/ASA”. Limitations to these negative studies include a 25% crossover rate between study arms, small sample size and

varying definitions of APS. Furthermore, no trial has evaluated prophylaxis in women with pregnancy loss and persistent anti-β2 glycoprotein antibodies. Given the poor quality evidence and mixed results for the use of LMWH/ASA prophylaxis in this setting, a large randomized trial is still needed.

When uncertainty exists in pregnancy, health care providers and patients often err on the side of treatment in hopes of preventing complications. Our goal is to minimize uncertainty, to provide clear recommendation to women with APS and pregnancy loss based on high-quality evidence. The full APPLE trial will compare the live birth rates in women assigned to the standard of care arm, prophylactic LMWH and ASA, compared to the experimental arm, ASA alone.

### **1.2 Why is a clinical trial needed now?**

Data from the TIPPS trial and two meta-analyses have recently shown that LMWH likely does not prevent pregnancy loss or complications in women with or without inherited thrombophilia. Given the poor-quality of existing evidence, evaluation of LMWH/ASA prophylaxis is still needed in APS patients. We conducted an online survey of 109 CanVECTOR Network and Thrombosis Canada physician members, 22 (20%) responded, and 91% would hypothetically approach a patient for enrollment in our trial, in either all (68%) or a subset (23%) of APS patients.

### **1.3 What are the risks with the standard of care regime of prophylactic LMWH/ASA?**

Downsides of LMWH include burden of injections (up to 400 injections/pregnancy), cost (\$4,000/pregnancy) and side effects of LMWH. In a systematic review of LMWH use in pregnancy, the most common side effects were bleeding (1.98%) which included significant antepartum bleeding, postpartum hemorrhage, and abdominal hematomas. Allergic skin reactions (1.8%) were also reported, some of which may be associated with HIT antibodies. Being on heparin lowers the likelihood that a woman receives epidural analgesia at the time of delivery, given the documented risk of epidural hematoma and associated hemiplegia when LMWH is not held prior to epidural analgesia. Serious and life-threatening complications of LMWH are rare, but possible. HIT has rarely been reported in pregnancy with the use of LMWH. The risk of osteoporosis and symptomatic fracture is rare, and significantly lower compared to unfractionated heparin.

### **1.4 What are the risks with the experimental arm (ASA alone)?**

As outlined in Section 1.0, given the poor quality of evidence in the LMWH/ASA arm, further evaluation of LMWH/ASA versus ASA is still needed. Based on data from meta-analyses and large randomized controlled trials, aspirin has no excess bleeding risk or neonatal complications in other populations of pregnant women, such as those with pre-eclampsia and women with prior pregnancy loss with or without inherited thrombophilia. There may be a possible small increased risk of gastroschisis with early exposure to aspirin.

A small randomized double-blind placebo controlled trial of 50 women with a history of recurrent pregnancy loss and positive antiphospholipid antibodies showed no difference in live birth rate or neonatal complications when treated with aspirin alone versus placebo during pregnancy. While a 'no treatment' arm could be considered for the experimental arm, there was a low proportion (23%) of physician acceptability of a no ASA arm in a national survey of CanVECTOR and Thrombosis Canada

members. Given the established safety profile of ASA in pregnancy and physician acceptability, ASA alone was chosen as the experimental arm.

### **1.5 Why is a pilot RCT needed before a full RCT can be completed?**

Because the use of antepartum prophylactic-dose LMWH and aspirin have become the standard of care in women with APS and past pregnancy loss, and is recommended in clinical practice guidelines, the recruitment of subjects into a randomized clinical trial may be challenging. Therefore, a pilot trial to assess feasibility is first needed.

### **1.6 Need for an open-label trial**

Because of initial poor recruitment in the TIPPS trial that evaluated LMWH in a double-blinded fashion (24 women enrolled after 3 years), the design of that trial was changed to open-label use of LMWH, which subsequently led to improved recruitment rates. Similarly, the pilot trial APPLE will use an open-label trial design to increase eligible women's acceptance of the trial and eliminate the burden of placebo injections. The primary endpoint in the larger multi-center trial is the live birth rate, which is objective and, therefore, not expected to change with the open-label use of LMWH.

### **1.7 Need for 'pragmatic' use of LMWH**

The use of prophylactic-dose LMWH and ASA has become the standard of care to prevent future pregnancy loss in women with APS, despite limited evidence for their use. Our pilot trial is looking at the feasibility of removing LMWH use in the antepartum setting, by comparing LMWH/ASA versus ASA alone. We recommend a "standard of care" regime of tinzaparin 4,500 IU sc daily until 20 weeks gestation, then tinzaparin 4,500 IU sc twice daily until 37 weeks gestation and aspirin 81 mg po daily until delivery. Treating physicians do have access to other LMWHs (dalteparin, enoxaparin) as standard of care, but this suggested regime with tinzaparin is recommended for consistency.

There is pharmacokinetic data in pregnant patients to suggest an increased dose after 20 weeks gestation is needed to maintain anti-Xa levels in the reference range, based on increased renal clearance later in pregnancy. While the recommended LMWH regime includes tinzaparin, pharmacokinetic data exists for all available LMWHs (dalteparin, enoxaparin).

### **1.8 Why are women with 2 losses included?**

The Sapporo Criteria definition of APS is based on a pregnancy loss definition of 1 late loss at  $\geq 10$  weeks gestation, or 3 recurrent early losses  $< 10$  weeks gestation. However, women are often referred for a question of thromboprophylaxis after 2 early pregnancy losses and with little evidence to guide therapy, it is not uncommon for physicians to offer antepartum LMWH/ASA prophylaxis after 2 losses. Knowing if ASA is as good as ASA/LMWH in women with 2 losses would be an important finding. The APPLE pilot trial will include women with 2 or more early pregnancy losses, in order to provide data for this important subgroup of women.

## **2. TRIAL OBJECTIVES**

### **2.1 Trial Purpose**

The purpose of this pilot trial is to determine the feasibility of conducting a multicenter randomized trial evaluating antepartum prophylaxis with ASA versus LMWH/ASA in women with confirmed APS and a history of late or recurrent early pregnancy loss.

Given the large sample size needed to adequately power a large multicenter trial that assesses the efficacy of ASA alone versus LMWH/ASA (section 8.2), we first need to determine if we can meet minimum recruitment rates needed for a full multicenter trial to be possible. To test this, we will open the trial at 2 centers with the goal of recruiting one patient every two months. The randomization design for the pilot feasibility trial is the same as the full trial, to best represent what actual recruitment rates and trial conditions would be like in the full trial. If the pilot feasibility trial is successful, then the secondary outcomes collected will be used in the analysis of the larger full multicenter trial.

The purpose of the full trial will be to determine the efficacy and safety of antepartum prophylaxis with aspirin alone to improve the live birth rate in women with confirmed APS and a history of late or recurrent early pregnancy loss, compared to the standard of care regime of LMWH/ASA prophylaxis.

### **2.2 Pilot Trial Objectives**

The primary objective of the pilot trial is the mean recruitment rate per center per month, calculated over 24 months.

Secondary objectives of the pilot trial will include evaluating:

- The feasibility of obtaining all required approvals/contracts in a timely fashion
- The number of patients who are ineligible based on the exclusion criteria
- The consent rate for eligible women who are approached
- The crossover rate between study arms
- The compliance rate of antepartum LMWH use
- Explore the reasons for non-consent among physician and patients

### **2.3 Pilot Trial Endpoints**

The primary feasibility outcome of the pilot trial is a mean recruitment rate of 0.5 subjects per center per month. The secondary feasibility outcomes of the pilot trial and associated *a priori* feasibility targets are as follows:

1. Proportion of sites requiring >18 months to obtain all required approvals/contracts from time of delivery of all study documents: <50%.
2. Proportion of screened patients who meet eligibility criteria (i.e. patients who meet inclusion criteria and are also eligible based on exclusion criteria): >30% of subjects
3. Proportion of eligible subjects who provide consent: >30% of subjects
4. Proportion of withdrawals/loss to follow-up among randomized patients: <10% of subjects
5. Crossover rate between standard of care and experimental study arms: <20%
6. Level of compliance with study drug: >80% compliance rate of total antepartum LMWH use
7. Reasons for physician and patient non-consent

## **2.4 Full Trial Objectives**

The primary objective of the full trial will be to determine the efficacy of ASA in improving live birth rate among women with APS and past pregnancy loss, compared to the standard of care arm of LMWH/ASA.

Secondary objectives of the full trial will include assessing the efficacy of ASA to prevent other pregnancy complications (pre-eclampsia, SGA, placental abruption, pre-term labor) and thrombotic complications (VTE, death from VTE, ATE) in women with APS and past pregnancy loss, versus LMWH/ASA. Safety data will also be reported, including bleeding and other adverse events.

## **2.5 Full Trial Endpoints**

The full trial endpoints will also be collected in the Pilot APPLE Trial. The primary full trial outcome is the livebirth rate. The secondary full trial outcomes are:

1. Livebirth rate according to central laboratory test results
2. Pregnancy loss by gestational age (<10 weeks, 10-19 weeks, ≥20 weeks)
3. Pre-eclampsia
4. Early onset pre-eclampsia
5. Severe pre-eclampsia
6. Small-for-gestational age (SGA) <10th percentile
7. SGA <5th percentile
8. SGA <3rd percentile
9. Placental abruption requiring delivery
10. Pre-term delivery <37 weeks gestation
11. Symptomatic venous thromboembolism (VTE)
12. Symptomatic arterial thromboembolism (ATE)
13. Major bleeding
14. Clinically relevant non-major bleeding
15. Peripartum major bleeding
16. Peripartum minor bleeding
17. Non-major non-CRNM bleeding
18. Heparin induced thrombocytopenia (HIT)
19. Symptomatic fracture
20. Allergic reaction
21. All-cause mortality

## **2.6 Endpoint Definitions**

### Livebirth

A birth in which a baby is born alive. If there are multiple births (i.e. twins) then it is counted as one live birth if at least one is born alive.

### Pregnancy loss by gestational age

Will record the pregnancy loss based on the gestational age in weeks. Will use the best information available to determine the gestational age at the time of the pregnancy loss. First, pathological examination of products of conception then ultrasound dating assessment at the time of pregnancy loss then medical documentation of timing of pregnancy loss then patient recall of timing of pregnancy loss. A pregnancy loss of one or more multiple births (i.e. twins) will be recorded.

Pre-eclampsia

Systolic blood pressure  $\geq$  140 mm Hg or diastolic blood pressure  $\geq$  90 mm Hg and proteinuria  $>0.3$  g/ 24 hours or  $\geq$  30 mg/mmol urinary creatinine in a spot (random) urine sample.

- a. Early onset pre-eclampsia: Pre-eclampsia  $<$  34 weeks gestation
- b. Severe pre-eclampsia: At least one criterion: systolic blood pressure  $\geq$  160 mm Hg or diastolic blood pressure  $\geq$  110 mm Hg, proteinuria  $>$  5 g/24 hours, AST, ALT, or bilirubin greater than 2xULN, platelets  $<$  100 x 10^9 /L, pulmonary edema, seizures (eclampsia), headache or other neurological manifestations (stroke, intracranial hemorrhage, cerebral edema, hyperreflexia and visual impairment), coagulopathy (elevated INR/PT or PTT greater than 1.5xULN or fibrinogen  $<$  2 g/L), oliguria ( $<$  30 mL/hour for 3 hours), or HELLP syndrome. HELLP syndrome requires 3 criteria: hemolysis [lactate dehydrogenase (LDH)  $>$  600 IU/L or serum bilirubin  $>$  1.2 mg/dL] an abnormal elevation of liver enzymes (AST or ALT greater than 2xULN) and platelets  $<$  100 x 10^9 /L.

Small-for-gestational age (SGA)

Percentile of birth weight determined using local gender and gestational age specific birth weight charts.

- a. SGA:  $<$  10th birth weight determined using local gender and gestational age specific birth weight charts.
- b. Severe SGA:  $<$  5th percentile of birth weight determined using local gender and gestational age specific birth weight charts.
- c. Very Severe SGA:  $<$  3rd percentile of birth weight determined using local gender and gestational age specific birth weight charts.

Placental abruption

Clinical diagnosis of placental abruption leading to delivery.

Pre-term delivery

Delivery at  $<$  37 weeks gestation.

Symptomatic VTE

VTE is defined as symptomatic deep vein thrombosis (DVT) or pulmonary embolism (PE). DVT is defined as a non-compressible segment or filling defect proximal to the calf trifurcation based on ultrasonography, venography or magnetic resonance imaging. PE is diagnosed by a new intraluminal filling defect on CT pulmonary angiogram (segmental artery or more proximal), a high probability perfusion defect on a ventilation-perfusion study based on PIOPED criteria with planar images, or PE as a definite or probably cause of death.

Symptomatic ATE

Symptomatic arterial events include ischemic stroke, transient ischemic attack, myocardial infarction, peripheral embolism, or death due to a vascular cause based on autopsy findings (excluding PE or intracranial hemorrhage).

Major bleeding

Clinical or radiographical evidence of bleeding associated with one of: with a fall in hemoglobin of 20 g/L (2 g/dL) or more; or a requirement for transfusion of two or more units of red blood cells or whole blood; or symptomatic bleeding occurring in a critical site: intracranial, intraspinal, intraocular, pericardial, intra-articular, intramuscular with

compartment syndrome, or retroperitoneal, or was considered to have contributed to maternal death.

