**AND**

Laboratory Criteria: At least **one** positive laboratory test listed below that is positive on **two** or more occasions at least 12 weeks apart\*\*\*:

- A. Presence of lupus anticoagulant (LAC)

- B. Anticardiolipin antibody (aCL) of IgG or IgM with a titre > 99th percentile or > 40 GPL or MPL
- C. Anti-β2 glycoprotein antibody of IgG and/or IgM with a titre > 99th percentile

Subjects can initially be eligible for enrollment and randomization if they only have one positive lab result. A second set of labs would be drawn 12 weeks apart from the first lab result, and if the second set is positive they will continue in the study. If the second set is negative, the subject will be withdrawn from the study.

\*Examples of explained miscarriage or fetal loss include: loss associated with severe congenital malformations, chromosomal abnormalities, neonatal alloimmune haemolytic anaemia, recent CMV infection, positive fetal or placental Listeria cultures, and women with known abnormal uterine anatomy.

\*\*Determining timing of pregnancy loss: in reviewing the past obstetrical history the investigator will use the best available information (First, pathological examination of products of conception then ultrasound dating assessment at the time of pregnancy loss then medical documentation of timing of pregnancy loss then patient recall of timing of pregnancy loss) to determine the gestational age at the time of pregnancy loss.

\*\*\*According to the diagnostic criteria of APS, diagnosis should be avoided if more than 5 years is separated between positive antibody testing and a clinical manifestation, such as pregnancy loss

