#### **4.2. Exclusion Criteria**

1. Greater than 11 weeks +6 days gestational age at time of randomization
2. Indication(s) for prophylactic or therapeutic-dose anticoagulation
  - a. Venous thromboembolism (VTE)
  - b. Arterial thromboembolism (ATE)
  - c. Small-vessel thrombosis
  - d. Mechanical heart valve
  - e. Other indication for prophylactic or therapeutic-dose anticoagulation, at the discretion of the treating physician
3. Contraindication to heparin or aspirin including:
  - a. History of known heparin or LMWH allergy
  - b. History of known aspirin allergy
  - c. History of HIT
  - d. History of osteoporosis
  - e. Major bleeding within 7 days\*.
  - f. Known thrombocytopenia, based on platelet count < 50 x 10^9/L in the previous 3 months
  - g. Known hepatic disease, based on a medical history of elevated liver enzymes (3x ULN) and/or bilirubin (2xULN) documented within the last 3 months
  - h. Known renal failure, based on Creatinine Clearance < 30 mL/min (Cockcroft Gault) in the previous 3 months
  - i. Known severe hypertension, based on SBP > 200 mmHg and/or DBP > 120 mmHg in the previous 3 months
4. Received 7 or more doses of LMWH
5. Previous participation in the trial

6. Geographic inaccessibility\*\*
7. Refused consent

\*All other active or recent bleeding is at the discretion of the treating physician.

\*\*At the discretion of the patient or the treating physician

Note: Subjects currently receiving aspirin are eligible for the study.

Please note: Investigators should use caution when prescribing LMWH to patients with a history of gastric ulceration or whom weight >120kg or <45kg.

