#### **4.3 Withdrawal of Subjects**

A subject has completed the study once all follow-up procedures have been completed.

Study drug is discontinued and appropriate clinical management is initiated in the case of the following outcome events (as defined in section 2.6). For the subjects who reach a study endpoint, LMWH and aspirin prophylaxis will be left up to the discretion of the treating physician, and documented.

1. Pregnancy loss
2. Pre-eclampsia
3. Placental abruption
4. Preterm delivery (<37 weeks)
5. VTE (objectively documented DVT, PE or sudden death)
6. Major bleeding
7. Thrombocytopenia (Platelet count <50 x 10^9/L)
8. Symptomatic fracture

In the event that the outcome does not result in infant delivery (ie. diagnosis of a VTE, fracture, thrombocytopenia, major bleed), antenatal follow-up will continue as scheduled in the protocol and data will be collected until 6 weeks post-partum or pregnancy related outcome.

A subject can be withdrawn from the trial treatment if, in the opinion of the investigator, it is medically necessary. This does not always correspond to study withdrawal – in which case antenatal follow-up will continue as scheduled in the protocol and data will be collected until the 6-12 weeks post-partum clinic visit, up until 6 weeks postpartum.

If the subject is prematurely discontinued from participation in the study, the study personnel will make every effort to obtain, and record, information about the reasons for discontinuation and any adverse events and if possible perform all safety assessments.

A subject may voluntarily withdraw participation in this study at any time, including for future data collection. If the subject does not return for a scheduled visit, every effort will be made to contact the subject. In any circumstance, every effort will be made to document the reason for withdrawal and when possible all safety assessments will be done.

[figure not shown]
All data will be reported for any subject randomized and not completing the study. Subjects withdrawn as a result of an adverse event thought to be related to the study drug will not be replaced. All safety data collected from all subjects during the study will be analyzed.

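### The pre-eclampsia definitions have no onset or worsening rule, so hypertension, proteinuria and laboratory values that eligibility allows can be counted as endpoints

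*Combined protocol and SAP*

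**What the plan says.** **Endpoint (Section 2.6).** Pre-eclampsia is a systolic pressure of at least 140 or a diastolic pressure of at least 90 mmHg, with proteinuria above 0.3 g/24 h or at least 30 mg/mmol "urinary creatinine in a spot (random) urine sample". Early onset means before 34 weeks. The severe form is introduced as "b. Severe pre-eclampsia: At least one criterion: systolic blood pressure" of 160 or more (or diastolic 110 or more). Its list continues with, among others, "AST, ALT, or bilirubin greater than 2xULN, platelets" below 100 × 10⁹/L, and "coagulopathy (elevated INR/PT or PTT greater than 1.5xULN" or fibrinogen below 2 g/L.

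**Entry (Sections 4.1 and 4.2).** One qualifying laboratory criterion is "Presence of lupus anticoagulant (LAC"). The matching exclusions are "Known severe hypertension, based on SBP > 200 mmHg and/or DBP > 120 mmHg in the previous 3 months"; "Known thrombocytopenia, based on platelet count < 50 x 10"⁹/L; liver enzymes at 3 times or bilirubin at 2 times the upper limit of normal (ULN); and creatinine clearance below 30 mL/min. Proteinuria is not an exclusion. Section 6.1 records hypertension and SLE at baseline, and neither excludes a woman apart from the blood pressure limit above.

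**Use of the definition.** Section 6.7 has blinded adjudicators judge suspected events against the protocol's criteria. Section 4.3 says "Study drug is discontinued and appropriate clinical management is initiated in the case of the following outcome events", refers to Section 2.6 for their definitions, and lists pre-eclampsia. Section 8.1.4 carries pilot outcomes into the full-trial analysis if the design does not change significantly.

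**The concern.** An endpoint meant to capture a complication arising during treated pregnancy should separate it from disease that was there beforehand. This definition does not. A woman with chronic hypertension and established proteinuria satisfies both elements without any change in her condition, and because early onset has no lower gestational limit she satisfies that too.

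The authors build newness in elsewhere: pulmonary embolism on CT requires a new filling defect (Section 2.6), and a pre-existing condition becomes an adverse event only if it worsens (Section 7.1). The second rule covers adverse events only.

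At stake are secondary full-trial endpoints 3, 4 and 5 in Section 2.5. Pre-eclampsia is also the first pregnancy complication named in the secondary objectives (Section 2.4). Because pilot data may be pooled, a definition changed later would mean re-adjudicating pilot events.

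**Working it through.** The plan gives no pre-eclampsia rate or power figure to reproduce, so the main check sets thresholds side by side.

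| Item | Endpoint criterion (2.6) | Excluded only if (4.2) | Eligible and meets criterion |
|---|---|---|---|
| Blood pressure, base | ≥140 or ≥90 | >200 and/or >120 | 140–200 or 90–120 |
| Proteinuria, base | >0.3 g/24 h or ≥30 mg/mmol | no limit (creatinine clearance <30 only) | any amount if clearance ≥30 |
| Blood pressure, severe | ≥160 or ≥110 | >200 and/or >120 | 160–200 or 110–120 |
| Platelets, severe | <100 × 10⁹/L | <50 × 10⁹/L | 50–99 |
| AST/ALT, severe | >2×ULN | 3×ULN | between 2× and 3×ULN |
| Bilirubin, severe | >2×ULN | 2×ULN | none |
| PTT, severe | >1.5×ULN | no limit | not bounded by eligibility |

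Both base elements can therefore be present at entry, and three severe criteria (blood pressure, platelets, AST/ALT) overlap with eligibility on the protocol's own figures. PTT is a separate case, because eligibility is silent on it.

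**Can a prior state be identified later?** Sections 6.1 and 6.2 and the Schedule of Mandatory Events list a blood count, creatinine and antiphospholipid tests at baseline. They list no blood pressure reading, urine protein, liver tests, INR or PTT. Prior platelets will be on record; the rest depends on the chart.

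**Dilution, as an illustration only.** Let *b* be the share of women in each arm counted as events because of pre-existing disease, and *p* the true rate among the others. The observed rate is *b* + (1 − *b*)*p*. None of these rates is in the documents.

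Assumed true rates 10% and 6% (ratio 0.60):
- *b* = 4%: (0.06 + 0.04 × 0.94)/(0.10 + 0.04 × 0.90) = 0.0976/0.1360 = 0.72
- *b* = 6%: (0.06 + 0.06 × 0.94)/(0.10 + 0.06 × 0.90) = 0.1164/0.1540 = 0.76

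Assumed true rates 15% and 10%, with 373 analysed per arm (828/2 × 0.90 = 372.6). Power is by normal approximation at two-sided alpha 0.05: Φ{[|p₁ − p₂| − 1.96√(2p̄(1 − p̄)/n)] / √[(p₁(1 − p₁) + p₂(1 − p₂))/n]}.

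| *b* | Observed rates | Ratio | Power |
|---|---|---|---|
| 0% | 15.0% v 10.0% | 0.67 | 54% |
| 2% | 16.7% v 11.8% | 0.71 | 48% |
| 5% | 19.25% v 14.5% | 0.75 | 41% |
| 10% | 23.5% v 19.0% | 0.81 | 32% |
| 15% | 27.75% v 23.5% | 0.85 | 26% |

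The direction is the same under both sets of rates. The size depends entirely on *b*, which is unknown.

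**The case against.** **Events must first be suspected.** Outcomes are collected from the 20 ± 4 week visit, extra tests are ordered when an outcome is clinically suspected (Section 6.2), and the committee sees only suspected outcomes. Stable hypertension with known proteinuria need not be referred. This stands against a reading that a reader might reach from the thresholds alone: that a woman becomes an endpoint, and has her treatment stopped, on the day of randomization. That follows only from the literal wording, not from the planned procedures. It does not protect the endpoint once a case is referred, because the written criteria do not ask what was present before.

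**Adjudicators would apply ordinary clinical sense.** They may, but Section 6.7 ties them to the protocol's criteria, and blinding does not supply a missing onset rule.

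**Severe is a subtype.** It is item (b) under pre-eclampsia, next to item (a), which names pre-eclampsia explicitly. On the natural reading, a low platelet count, raised enzymes or a long PTT alone creates no event; it only upgrades one. This stands, although the text does not say that the base definition is required.

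**The lupus anticoagulant link is not in the documents.** That it, or heparin, may prolong PTT is general laboratory knowledge. The documents give no frequency above 1.5×ULN, and PTT is not a scheduled test. This stands, so the point is a missing exception of unknown consequence.

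**Stakes are modest.** These are 3 of 21 secondary endpoints of a possible later trial. This also stands.

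**Conclusion.** The definition can count pre-existing disease as pre-eclampsia and early-onset pre-eclampsia, and can let pre-existing blood pressure, platelet or enzyme values turn an event into a severe one. Randomization balances such states on average, so the expected effect is misclassification and dilution toward no difference, of unknown size. The ratios above show direction only. The pilot's recruitment endpoint, live birth and the full-trial sample size of 828 are not affected.

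Three further inferences go beyond the documents:
- *That false events concentrate in the high-risk stratum.* Section 5.2 also defines that stratum by anticardiolipin above 40 GPL or MPL, or by anti-β2 glycoprotein positivity. Only the PTT item has any link to lupus anticoagulant, and it bears on one endpoint. Nothing ties prior hypertension or proteinuria to the stratum.
- *That more than three severe criteria overlap with eligibility.* Systolic and diastolic pressure form one item.
- *That heparin biases severe pre-eclampsia against the LMWH arm.* Heparin use does differ by arm, and Section 6.3 foresees unfractionated heparin after 37 weeks. But nothing in the documents shows how often the PTT threshold would be crossed.

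Separately, a woman eligible under Section 4.2 can literally meet a Section 4.3 stopping event. Those passages need reconciling whatever the size of the dilution.

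**What to change.** In Section 2.6 and the adjudication form:

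1. Require new hypertension plus new proteinuria at or after 20 weeks. Where either was already present, require documented worsening from the early-pregnancy value.
2. State that severe pre-eclampsia requires pre-eclampsia plus a listed feature that was not already present to the same degree.
3. Do not let PTT alone qualify as coagulopathy in women with lupus anticoagulant or on heparin. INR and fibrinogen remain.
4. Take prior values from the chart and state how a missing one is handled, for example by treating the feature as new and flagging it for a sensitivity analysis.

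Sections 2.6, 4.2 and 4.3 must be reconciled. Section 4.3 takes its definitions from Section 2.6, so editing the endpoint also alters the stopping trigger. The investigators should settle that deliberately; this review takes no position on the clinical rule.

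The cost is wording, one form, and chart abstraction of early-pregnancy blood pressure, urine protein, liver and coagulation values. No visit or test is added. The price is that some prior values will be missing, which is why the fourth item is needed. Making the change before pilot events are adjudicated avoids reviewing them twice.
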